impairments in type-token ratio and speech productivity. These findings illustrate the potential utility of VLSM for investigating the connection between treatment-induced changes in language performance measures (such as the PNT) and the degree of cortical and subcortical involvement, as hypothesized under Specific Aim 1.

C. Methods and Research Plan:

The proposed study will employ a within-subject repeated measures design to establish the functional relationship between amount of treatment and treatment response. We will also randomize half of the sample to a delayed treatment condition in order to control for the effects of social contact associated with PIRATE participation. Finally, we will supplement this design with between-subjects analyses designed to measure how different randomly-selected samples of participants respond to varying amounts of treatment. Study

participants will receive intensive semantically-oriented naming treatment in the context of the PIRATE program. Their response to treatment will be measured and compared across the 4-week duration of PIRATE using probes of treated and untreated stimuli as well as a standardized measure of naming performance. This comparison will address Specific Aim 2, to identify the dose-response relationship for aphasia therapy. Measures of naming gains in response to treatment will be compared across groups of participants defined in terms of their language-impairment profiles, to determine whether semantically-oriented naming treatment benefits all or only a subset of individuals with naming deficits. The study will also employ voxel-based lesion symptom mapping analyses to examine the relationship between lesion site and extent and treatment response, as well as regression analyses to examine the relationship between cognitive factors and treatment response. These analyses will together address Specific Aim 1, to identify psycholinguistic, cognitive, and neuroanatomical predictors of positive response to intensive semantically-based naming treatment.

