The first analysis will evaluate whether the social contact associated with PIRATE participation results in improved performance on study measures, independent of any actual aphasia treatment. We will use a multivariate mixed model to test whether there are any differences between the immediate-treatment and delayed-treatment groups at the initiation of treatment, and whether there is any group-by-time interaction suggesting a positive effect of the delayed treatment week. The dependent variables will include performance on treated and untreated naming probes and PNT short forms.

If this analysis finds no significant differences between the groups, it will suggest that any observed treatment gains can be attributed to the SFA treatment rather than general effects of the social contact associated with PIRATE. In this case, the two groups will be collapsed for further analysis. In the unexpected event that this analysis finds a significant difference favoring the delayed treatment condition, it will suggest that observed treatment gains should be attributed to the combination of SFA and the socialization inherent in a residential treatment program, rather than to SFA alone. In this case, we will use the data to estimate the size of the socialization effect and statistically control for it in subsequent analyses, where possible.

C.3.1 Psycholinguistic, cognitive, and neuroanatomical predictors of treatment response

The primary dependent variable for analyses relevant to Specific Aim 1 will be the proportion of correctly-named treated stimuli at study exit (post-treatment), minus the proportion of correctly-named treated stimuli at study entry (pre-treatment). This difference score provides the simplest measure of naming treatment response. Supplementary analyses may be carried out using a related dependent variable, the percentage of possible naming improvement^[10]. This is a derived measure which divides the simple pre-post difference score

by the difference between pre-treatment naming performance and ceiling performance (100% accuracy minus observed pre-treatment accuracy). This measure helps correct for observed differences in baseline accuracy.

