Secondary dependent variables for these analyses will include accuracy on untreated related stimuli (accuracy at study exit minus accuracy at study entry) and Rasch-scaled scores for PNT stimuli (scores at exit minus scores at entry). Previous studies have not found any predictive relationships between neuroanatomical or other variables and generalization to untrained stimuli^[9, 20]. However, those studies did not administer treatment in the amounts or intensities provided in PIRATE or in the proposed research. It is possible that more intensive and/or larger doses of aphasia treatment may uncover stronger generalization effects (as well as stronger predictive relationships) than have previously been reported.

C.3.1.1 Group effects on treatment response

Participants will be classified as having primarily phonological, primarily lexical-semantic, or mixed naming impairments, using the methods described in section C.2.3 above. A between-participants analysis of variance will be carried out on the primary and secondary dependent measures of treatment response, with language-impairment group as an independent variable. As predicted by Hypothesis 1a and consistent with previous findings in the naming-treatment literature^[12, 44], we anticipate that there will not be a main effect of language-impairment group on treatment response. The different groups of naming-impaired individuals will show comparable benefit from intensive, semantically-oriented naming treatment. If group differences are found in the ANOVA, we will explore their source using Tukey's multiple comparisons to control type-I error.

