To determine whether the proposed sample size will be sufficient to detect these between-group differences, a power analysis was carried out based on data from Wambaugh et al.^[12] and Abel et al.^[44]. Together, these two studies provide pre-treatment and post-treatment naming probe data for four aphasic participants classified as having primarily semantic impairment, four participants classified as having primarily phonological impairment, and one patient with mixed impairments, all of whom received semantically-oriented naming treatment. As noted above in section A.1, the effects of psycholinguistic profile on response to semantically oriented treatment were potentially counter-intuitive: there was better response in phonologically impaired vs. semantically impaired participants. Nevertheless, we used the pre-treatment/post-treatment probe data from these 9 patients to estimate the variance in change scores. We assume that a 20 percentage-point difference in treatment effect (i.e., an average of 2 items, given the 10-item probe sets) is needed for the effect to be considered clinically meaningful. Assuming that 12 of the anticipated 50 participants will have primarily semantic impairments and 12 will have primarily phonological impairments, the proposed between-subjects ANOVA will have power of 0.82 to detect a 20-percentage point difference between these two groups.

If no group differences are found in treatment response, as predicted under Hypothesis 1a, the treatment-response data will be collapsed across language-impairment groups for subsequent analysis. If group differences in the magnitude of treatment response are found, separate analyses for the relevant groups will be carried out for the cognitive and neuroanatomical hypotheses, in the analyses described below.

C.3.1.2 Prediction of treatment effects by cognitive factors

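### A non-significant ANOVA across impairment groups is read as the predicted comparable benefit, although it cannot show comparability and the plan's 20-point figure is never applied to the result

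*Combined protocol and SAP*

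**What the plan says.** Section C.3.1.1 classifies participants into three impairment groups and compares their change scores with a between-participants ANOVA. The prediction is an absence: "we anticipate that there will not be a main effect of language-impairment group on treatment response". The next sentence restates it as similarity: "The different groups of naming-impaired individuals will show comparable benefit from intensive, semantically-oriented naming treatment". Tukey comparisons follow only if the ANOVA finds a difference.

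The sample-size paragraph of the same section says that a 20-percentage-point difference in treatment effect "is needed for the effect to be considered clinically meaningful". With 12 semantic and 12 phonological participants among 50, it states "power of 0.82 to detect a 20-percentage point difference between these two groups". The 20 points is not used again.

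The ANOVA then decides what follows: "If no group differences are found in treatment response, as predicted under Hypothesis 1a, the treatment-response data will be collapsed across language-impairment groups". If differences are found, "separate analyses for the relevant groups will be carried out for the cognitive and neuroanatomical hypotheses".

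The opening of section C gives the purpose of the group comparison as "to determine whether semantically-oriented naming treatment benefits all or only a subset of individuals with naming deficits". Section A.1.1 likewise describes Hypothesis 1a as benefit in all three groups. The primary outcome, in C.3.1, is the "proportion of correctly-named treated stimuli at study exit (post-treatment), minus the proportion of correctly-named treated stimuli at study entry".

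**The concern.** The prediction is that something is absent, and the plan counts failure to reject as agreement with it. Under that rule noisier data make the predicted result more likely. Nothing in the section asks how large a difference the data still allow, although the plan has a yardstick for that question.

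A second gap concerns benefit itself. Three groups with equal gains could all have gained nothing, and the ANOVA would look the same. No gain per group with an interval is planned.

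Aim 1 asks for whom the treatment works, so this comparison is one of its main answers. The same test also decides whether the later predictor analyses use everyone together or are split by group, and two of those groups would have about 12 participants each.

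**Working it through.** **Inputs.** From C.3.1.1: 12 semantic, 12 phonological, 50 in total, so 50 − 12 − 12 = 26 mixed if all are classified; 20 points; power 0.82. From A.1.1: pilot gains of 37 points (SD 17, n = 4, phonological), 20 points (SD 9, n = 4, semantic) and 33 points (n = 1, mixed). Assumed, because C.3.1.1 does not state it: two-sided alpha 0.05. The SD behind 0.82 is not stated either.

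**The plan's power figure.** The pooled pilot SD is √[(3 × 17² + 3 × 9²)/6] = √185 = 13.6. The SD over all nine patients, rebuilt from the group summaries, is 14.6. Power at 20 points is then:
- SD 17, semantic v phonological: 0.822 (normal), 0.806 (t, 47 df), 0.786 (t, 22 df)
- SD 14.6, omnibus F with the mixed mean midway: 0.837
- SD 13.6, semantic v phonological: 0.93 to 0.95

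So 0.82 is attainable but cannot be confirmed without the SD and alpha. The steps below therefore calibrate the SD to 0.82.

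**Miss rate at 20 points.** 1 − 0.82 = 0.18. Each miss would carry the label of the predicted result.

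**What a non-significant result can leave open.** The standard error of the semantic-phonological difference is SD × √(1/12 + 1/12) = 0.408 × SD.
- Pairwise, the largest non-significant gap is t(0.975) × SE, with t = 2.074 (22 df) or 2.012 (47 df).
- Omnibus, mixed mean midway: between-group sum of squares = 2 × 12 × (d/2)² = 6d². With the critical F(2, 47) = 3.195, the largest d is SD × √(2 × 3.195/6) = 1.032 × SD.
- Omnibus, mixed mean equal to one of the other two: sum of squares = (38 × 12/50)d² = 9.12d². The largest d is SD × √(2 × 3.195/9.12) = 0.837 × SD.
- The 90% half-width is t(0.95) × SE, with t = 1.717 (22 df) or 1.678 (47 df, also used for the omnibus rows).

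| Reading of 0.82 | SD giving 0.82 | Largest non-significant gap | 90% half-width | Upper limit |
|---|---|---|---|---|
| Omnibus F, mixed midway | 14.9 | 15.4 | 10.2 | 25.6 |
| Omnibus F, mixed at one extreme | 18.4 | 15.4 | 12.6 | 28.0 |
| t-test, 12 v 12, 22 df | 16.3 | 13.8 | 11.4 | 25.2 |
| Contrast, 47 df | 16.7 | 13.7 | 11.4 | 25.1 |

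These rows take the observed SD to equal the calibrated one. At the pilot SD of 13.6 the upper limit is 20.5 (contrast, 47 df), 20.7 (mixed at one extreme) or 23.4 (mixed midway). It is above 20 each time, though only just at the low end.

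**Smaller true differences.** The pilot gap is 37 − 20 = 17 points. If that were the truth, a pairwise test would be non-significant in about 15% to 35% of trials (SD 13.6 to 17). At a true 10 points the figure is about 58% to 72%.

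**Benefit per group.** With 12 participants, a 95% half-width for a group's mean gain is t(0.975, 11 df) × SD/√12, about 8.6 points at SD 13.6 and 10.8 at SD 17. A useful estimate is therefore available from the planned sample.

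**The case against.** The plan says what it anticipates and when it will pool; it does not say that it will declare equivalence. It powers the test for a difference it calls clinically meaningful, so a null result carries information, and 18% is an ordinary type II error. All of that stands. Even so, power is fixed before the trial and does not show what the observed data exclude. The power statement also covers only one of the three pairs.

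Gain is tested elsewhere: the trend and weekly contrasts in C.3.2 cover the treated probes. Those analyses use the whole sample and are not planned by impairment group, so they do not say whether each group benefits.

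A reader might go further and infer that Hypothesis 1a is formally an equivalence hypothesis. The supplied text does not contain the hypothesis in full: A.1.1 words it as benefit in each group, and the language of comparability comes from C.3.1.1.

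A reader might also infer that the plan's 20 points supplies a ready equivalence margin, with a pass/fail rule at ±20 limiting false claims to 5%. The documents do not support this. The 20 points was set as a difference to detect, it equals the semantic group's whole pilot gain, and the pilot gap of 17 points lies inside it. The 5% limit also needs equal variances. With SDs of 9/9/17 (semantic/mixed/phonological; the mixed SD is assumed) and the mixed mean midway, simulation of an all-pairs 90% interval rule with a pooled SD declares comparability in about 8% of trials at a true 20 points. With Welch intervals it is 4.9%.

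**Conclusion.** The point holds as one about inference. The plan lets a non-significant ANOVA stand as the predicted comparable benefit and pools on it, without asking whether 20 points has been excluded. At a true 20-point semantic-phonological difference this goes wrong in about 18% of trials, which follows directly from the stated power. A result labelled as predicted can leave differences of about 25 to 28 points inside a 90% interval when the SD is calibrated to 0.82, and just over 20 points at the pooled pilot SD. These limits rest on groups of 12/26/12 and two-sided alpha 0.05; the unstated SD changes their size but not the conclusion. The benefit-in-each-group question is left without a planned estimate.

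The finding does not show that the power figure is wrong, that the sample is too small, or that a formal equivalence test is required. It should be fixed before the group results are interpreted.

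**What to change.** In C.3.1.1, for the primary treated-item change score:
- Report every pairwise group difference with an unequal-variance (Welch) confidence interval at a level stated in advance, read against the plan's 20 points.
- Report the mean gain with a 95% interval in each of the three groups.
- Do not describe a non-significant ANOVA as supporting comparable benefit. If an interval includes differences of 20 points or more in either direction, state that a clinically meaningful difference was not excluded.
- Make a formal comparability verdict optional, and only if the investigators justify a margin beforehand.

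For untreated probes and the PNT, where no meaningful group difference is given, report differences with intervals and make no comparability claim.

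In C.3.1.2, keep all participants in one regression with a group term whatever the ANOVA shows, and treat group-by-predictor interactions as exploratory. The choice of primary lesion-mapping analysis is left to the investigators.

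The cost is wording only, with no extra patients. The group term uses 2 degrees of freedom. The honest answer will often be inconclusive. As a guide, an all-pairs 90% interval rule at ±20 with a pooled SD is inconclusive in 7%, 12%, 31% and 43% of trials with truly equal groups (SD 13.6, 14.6, 17 and 18.4). At a true 10-point difference, with the mixed mean midway, it is inconclusive in 46% to 70% over the same SDs.

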Some participants may also have co-occurring conditions which would prevent them from participation in the imaging arm of the study (claustrophobia; presence of metal in the body). These participants will be enrolled in the study but will not complete imaging procedures. A chart review of PIRATE participants to date indicates that approximately 20% of veterans enrolled in PIRATE may have such exclusionary criteria: roughly 17% report pacemaker or other implanted metal objects or devices incompatible with MR scanning. Thus, the participant sample used to address the neuroanatomical hypotheses proposed under Specific Aim 1 may be smaller than the sample contributing data the other proposed analyses. Under the worst case scenario of no overlap between these imaging-related exclusionary criteria and those described in the preceding paragraph, we expect to obtain a sample size of 40 participants (50 minus 20%) to conduct the proposed imaging-related analyses. As described in section C.3.1.3 below, this sample size should be sufficient to detect the relationships relevant to the neuroanatomical hypotheses.

C.2 Procedures

The schedule of procedures for participants enrolling in the study is summarized in the flowchart in Figure 4. Participants enrolling in the research study will receive a single pre-treatment structural MRI and a battery of cognitive assessments at program entry (see section C.2.3 below). They will also have their performance on standardized measures of naming and other language functions assessed repeatedly throughout the protocol (see section C.2.2 below), and they will receive an intensive dose of a treatment (SFA) designed to target lexical-semantic processes (see section C.2.1 below). Participants' performance on treated and untreated lexical items will be probed three times weekly, to assess acquisition and generalization and to decide when participants will move to a novel set of treatment exemplars.

Half the participants will be randomly assigned to a delayed-treatment condition. The purpose of this condition is to provide an additional measure of experimental control, to ensure that any observed improvements are not due simply to the social contact afforded by the residential component of the treatment program. Previous work [7] has found that simple exposure or engagement in the absence of specific therapy

[figure not shown]

Figure 4: Testing and treatment procedures for study participants

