We will use the MRICron program's nonparametric lesion mapping (NPM) feature to complete the lesion symptom correlations^[106]. These data will be structured such that there is a binary classification at the voxel level (i.e., ±lesion) and continuous behavioral data (change score associated with the different outcome measures: PNT scores and scores on acquisition/generalization probes). Since these data are likely not to satisfy parametric statistical assumptions, we will use the NPM program's Brunner-Munzel nonparametric test to relate behavioral performance on each of the treatment-outcome predictors (change scores) to lesion distributions^[107-109]. We will apply a cluster threshold of 10 contiguous voxels and threshold for a false discovery rate of .05 in order to control for type I error while maintaining sufficient power to detect effects. We will also include voxels that have at least a 25% lesion overlap across patients. VLSM analyses will focus on four principal regions of interest (ROIs): left anterior cortex, left posterior cortex, left basal ganglia, and left hippocampus. Previous work (reviewed in section B.2 above) has shown that positive response to aphasia treatment is associated with intact left hippocampus and left basal ganglia. In addition, some previous work suggests that negative treatment response is associated with more intact left anterior cortex^[21], but other work suggests that greater recruitment of left anterior cortex is associated with positive treatment response^[23]. Additional work has also found that more intact left posterior cortex is associated with more positive treatment response^[23].

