To determine whether the proposed sample size will be sufficient to detect the lesion-behavioral correlations described above, a power analysis was carried out on the correlational data from Parkinson and colleagues^[21]. The correlation coefficients reported by Parkinson range from 0.65 to 0.85. Power analysis indicates that a sample size of 40 will provide power >0.99 for detecting effects of this magnitude and power of 0.80 for detecting correlations with r values of 0.38 or greater. Given the likely greater variability among the patients who participate in PIRATE, both in terms of their demographic characteristics and their language impairment profiles, we anticipate that any correlations between neuroanatomical markers and language performance and recovery may be somewhat weaker than those observed in the Parkinson and colleagues study^[21], which had a much more uniform sample. However, the projected sample size of 40 should be sufficient to detect weaker correlations than those observed by Parkinson and colleagues^[21].

If no significant correlations are found between the above ROIs and change scores for the outcome measures, we will perform additional VLSM analyses to examine the relationship between lesion site and extent and treatment response in subgroups of study participants. Since participants in this study will likely be more heterogeneous than those in previous studies, the data from the current study may be noisier due to greater inter-subject variability. To explore the effects of this variability on neural correlates of treatment response, participants will be divided by aphasia severity, their CAT T-scores, since different aphasia severities may be associated with different responses to treatment^[1]. Additional analyses may explore the lesion-treatment relationships found in different subgroups of veterans.

C.3.2 Dose-response analyses

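### A difference in mean response between impairment groups would trigger separate cognitive and lesion analyses, with much lower power for moderate effects and no test that predictors act differently by group

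*Combined protocol and SAP*

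**What the plan says.** Section C.3.1.1 compares treatment response across semantic, phonological and mixed impairment groups by ANOVA. If no difference is found, as Hypothesis 1a predicts, the groups are pooled for the later analyses. Otherwise, "separate analyses for the relevant groups will be carried out for the cognitive and neuroanatomical hypotheses". The relevant groups are not defined. The only group sizes given are in the ANOVA power statement: "Assuming that 12 of the anticipated 50 participants will have primarily semantic impairments and 12 will have primarily phonological impairments".

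The sample-size statements for the later analyses assume pooled samples. Section C.3.1.3 says of lesion correlations that "a sample size of 40 will provide power >0.99 for detecting effects of this magnitude", where the cited coefficients "range from 0.65 to 0.85", and adds "power of 0.80 for detecting correlations with r values of 0.38 or greater". Section C.1 derives the 40 as 50 less 20% who cannot be scanned. Section C.3.1.2 gives no power figure for the cognitive regressions, only an expectation that 50 participants will be enough. No power is given for any split analysis.

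**The concern.** The ANOVA asks whether average gain differs by group, which is a difference in intercepts. Hypotheses 1b and 1c ask how gain varies with cognition or lesion, which is a matter of slopes. Groups can differ in average gain and share the same slopes. The rule lets the first result decide how the second question is analysed, and no predictor-by-group interaction test stands between them.

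At stake are two of the three hypotheses under Specific Aim 1. In small strata a real predictor is easily missed. A predictor significant in one group and not in another is easily read as group-specific when the difference is chance.

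The plan handles a parallel case differently. In the introduction to section C.3, a difference favouring the delayed-treatment condition leads to statistical adjustment where possible, not to separate analyses.

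**Working it through.** **Inputs**
- Total 50, with 12 semantic and 12 phonological (C.3.1.1). The remainder, 50 − 24 = 26, is derived and not stated.
- Scanned sample 40 (C.1). If the 20% loss is proportional (assumption), 0.8 × 12 = 9.6 and 0.8 × 26 = 20.8. Held to the plan's total of 40, that is about 10, 10 and 20.
- Effects: r = 0.38, and the range 0.65 to 0.85 (C.3.1.3).
- The alpha and sidedness of the lesion power statement are not given. I assume 0.05 and show both.

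**Formula.** Fisher z: power = Φ(atanh(r) × √(n − 3) − z), with z = 1.645 one-sided or 1.96 two-sided. Simulation of the sample correlation under bivariate normality is the check.

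**The plan's own figures, n = 40**
- r = 0.38: atanh(0.38) × √37 = 0.400 × 6.083 = 2.434. One-sided, Φ(0.789) = 0.785 (simulated 0.80). Two-sided, Φ(0.474) = 0.68 (simulated 0.69). The stated 0.80 therefore reproduces one-sided only.
- r = 0.65: 0.997 two-sided, so the claim of more than 0.99 reproduces.

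**Separate groups, simulated power, one-sided (two-sided)**

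| n | r = 0.38 | r = 0.65 |
|---|---|---|
| 10 (scanned, small groups) | 0.30 (0.19) | 0.71 (0.58) |
| 20 (scanned, largest group) | 0.52 (0.39) | 0.95 (0.91) |
| 12 (cognitive, small groups) | 0.35 (0.23) | 0.79 (0.68) |
| 26 (cognitive, largest group) | 0.63 (0.50) | 0.98 (0.97) |

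The Fisher formula agrees closely at r = 0.38: 0.28 (0.18) at n = 10 and 0.50 (0.38) at n = 20. At r = 0.85, n = 10 keeps 0.97 (0.94).

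The smallest r with 80% power is 0.71 (0.76) at n = 10 and 0.53 (0.58) at n = 20, against 0.38 (0.43) at n = 40.

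**If only one group of 12 is split off**
- Cognitive sample: the larger stratum is 50 − 12 = 38, with power 0.78 one-sided at r = 0.38.
- Lesion sample: the larger stratum is about 40 − 10 = 30. The formula gives 0.400 × √27 = 2.079, hence Φ(0.434) = 0.67 one-sided and Φ(0.119) = 0.55 two-sided.

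**Full sample with a two-degree-of-freedom group term, common slope, r = 0.38**
- Lesion, n = 40: 0.78 (0.67), against 0.80 (0.69) without the term.
- Cognitive, n = 50: 0.86 (0.77), against 0.87 (0.79) without the term.

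All lesion figures are for a single correlation before voxel-wise false discovery rate control, so they are optimistic in every column.

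**The case against.** **The branch is a contingency.** The plan predicts no group difference, and its power statements are made for the pooled case. This stands. The branch is still not remote. Section A.1.1 reports average gains of 37 points (SD 17) in phonological and 20 (SD 9) in semantic impairment, four people each, and the plan claims power of 0.82 to detect a 20-point difference.

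**A three-way split is not stated.** With the relevant groups undefined and Tukey comparisons used to locate differences, one group might be separated and the rest kept together. This also stands, and the loss is then smaller, as shown above.

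**The claimed power is not removed altogether.** A reader might infer that it is. The documents do not support that. No power figure is claimed for the cognitive analysis. For lesions, the largest group keeps 0.91 two-sided at r = 0.65, and even 10 people keep 0.94 at r = 0.85. The serious loss is at moderate correlations, and in the small groups at r = 0.65.

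**The voxel test is not arithmetically blocked at n = 10.** With 3 lesioned and 7 not, the smallest exact two-sided rank p-value is 2/120 = 0.017, and a reader might conclude that false discovery rate control could hardly be met. That floor belongs to an exact permutation test. The plan names Brunner-Munzel and mentions no exact p-value. With its usual t approximation, a 3 v 7 arrangement with one rank out of order gives p = 0.0005. Whether that approximation is sound at this size is another question. Also, 25% overlap is a minimum, so some voxels would be better balanced.

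**Adjustment is not free.** The 1 to 2 points assume that group is unrelated to the predictors. If group explained 25% of predictor variance (assumption), two-sided Fisher power at r = 0.38, n = 40 would fall from 0.66 to 0.54; at 10% it would be 0.61 and at 40% about 0.45. This stands but does not favour the plan's rule, because within-group analyses discard the same between-group variation. Interaction tests with groups of 12 will also have little power.

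**Conclusion.** The concern holds for the rule as written. A difference in mean response is not grounds for replacing the pooled tests of Hypotheses 1b and 1c, and no interaction test is planned to supply such grounds.

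The size depends on the branch being entered and on how many groups are separated. With a three-way split and proportional imaging loss, lesion power at r = 0.38 falls from 0.80 to about 0.3, 0.3 and 0.5 one-sided, or from 0.69 to about 0.2, 0.2 and 0.4 two-sided. At r = 0.65 the stated power of more than 0.99 is not met in any scanned group, though the largest keeps more than 0.9. For the cognitive analysis the per-group figures are similarly low at r = 0.38 (about 0.35 in groups of 12 and 0.63 in the group of 26, one-sided), but there is no stated figure to set them against.

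**What to change.** Replace the splitting rule in section C.3.1.1 with the following:
- Whatever the ANOVA shows, the full-sample analyses remain the tests of Hypotheses 1b and 1c.
- The cognitive regressions include impairment group as a factor.
- Brunner-Munzel takes no covariate, so the VLSM analysis uses change scores centred within impairment group, or a lesion model that accepts covariates.
- A group-specific claim is made only after a predictor-by-group interaction test. Within-group estimates are reported as description, with confidence intervals where the method gives them.

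This is a short change to the analysis text and needs no new data. It costs about 1 to 2 points of power for the group term, and more if group is correlated with the predictors, a loss that separate analyses would also incur. The interaction test will have low power at these group sizes, so a non-significant result should not be read as showing equal slopes.
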